6.5.3 Random-slopes Model

The specification of the random-slopes linear mixed model and the primary linear contrast for estimating differences in mean rate of progression in a given continuous efficacy endpoint (ALSFRS-R total and domain scores, SVC, HHD upper extremity, lower extremity, and global average percentages, FVC by home spirometry, quantitative voice characteristics, serum creatinine, serum NfL, ALSAQ-40 domain scores and SI, CNS-BFS total score, and CNS-LS score) are revised from those specified in the M-SAP to include a main effect of treatment and main effects of centered baseline Nuedexta use, centered site of symptom onset (bulbar vs. non-bulbar), and their interactions with visit as additional covariates and to specify that study months are calculated as the difference in days from the Baseline Visit to the date of assessment of a given endpoint multiplied by 12 / 365.25.

The model will include fixed terms for month since the Baseline Visit, treatment group, treatment group × month interaction, centered years since ALS symptom onset and centered years since ALS symptom onset × month interaction, centered delta-FRS and centered delta-FRS × month interaction, centered baseline riluzole use and centered baseline riluzole use × month interaction, centered baseline edaravone use and centered baseline edaravone use × month interaction, centered baseline Nuedexta use and centered baseline Nuedexta use × month interaction, and centered site of symptom onset (bulbar vs. non-bulbar) and centered site of symptom onset × month interaction. The following equations describe the model with regimen random effects:

$$\begin{aligned}
 Y_{ij} &= \gamma_1 + a_{k(i)}^0 + b_i^0 + \gamma_2 t_i + \boldsymbol{\gamma}'_3 \mathbf{z}_i \\
 &+ (\gamma_4 + a_{k(i)}^1 + b_i^1 + \gamma_5 t_i + \boldsymbol{\gamma}'_6 \mathbf{z}_i) m_{ij} + \epsilon_{ij} \quad (\text{eqn. 2}) \\
 \{a_k^0, a_k^1\} &\sim N(\mathbf{0}, \boldsymbol{\Sigma}_r), \{b_k^0, b_k^1\} \sim N(\mathbf{0}, \boldsymbol{\Sigma}_p), \epsilon_{ij} \sim N(0, \sigma_\epsilon^2) \\
 \text{Cov}(\mathbf{a}_k, \mathbf{b}_k) &= \mathbf{0}, \text{Cov}(\mathbf{a}_k, \boldsymbol{\epsilon}_{i\cdot}) = \mathbf{0}, \text{and } \text{Cov}(\mathbf{b}_k, \boldsymbol{\epsilon}_{i\cdot}) = \mathbf{0}
 \end{aligned}$$

where Y_{ij} is a given efficacy endpoint measured in participant i at visit j , $a_{k(i)}^0$ and $a_{k(i)}^1$ are random intercept and slope for regimen k to which participant i was assigned, b_i^0 and b_i^1 are random intercept and slope for participant i , \mathbf{z}_i is the vector of covariates (centered time since onset, centered delta-FRS, centered baseline riluzole use, centered baseline edaravone use, centered baseline Nuedexta use, and centered site of symptom onset) for participant i , m_{ij} is the time from baseline to observation j for participant i in months calculated as days x 12 / 365.25, t_i is an indicator variable for treatment t to which participant i was assigned, $\gamma_1, \gamma_2, \gamma_3, \gamma_4, \gamma_5$, and $\boldsymbol{\gamma}_6$ are estimated parameters and vectors of parameters for the fixed effects, and ϵ_{ij} is the residual for observation j for participant i . The regimen-specific random effects are normally distributed with mean $\mathbf{0}$ and unstructured covariance matrix $\boldsymbol{\Sigma}_r$. The participant-specific random effects are normally distributed with mean $\mathbf{0}$ and unstructured covariance matrix $\boldsymbol{\Sigma}_p$. The residuals for a

given participant are normally distributed with mean 0 and variance σ^2_ϵ . The regimen-specific random effects, participant-specific random effects, and residuals are uncorrelated.

The following SAS code specifies the model:

```
proc mixed data=xxx method=reml;
  class regimen id trtrnd;
  model Value = trtrnd|month
              sx2b1|month dFRS|month r1z|month edv|month
              NDX|month bulbar|month / solution cl;
  random intercept month / subject=regimen type=un;
  random intercept month / subject=id type=un;
```

where month is time in months from the Baseline Visit (assuming 12 months in an average of 365.25 days per year) and other fields are the same as identified above in Section 6.5.2. The primary estimand will be the treatment-dependent difference in slopes. The estimate and its 95% Wald confidence bounds will be obtained by a linear contrast of adjusted means. The following SAS code specifies the linear contrast for a regimen with one active treatment assuming that the sort order for treatment group has the active group last:

```
estimate "3|Act vs Plb|Slope (/mn)" month 0 trtrnd*month -1 1 / cl;
```

A significant difference in slopes in the direction of greater improvement or less worsening among participants randomized to active treatment would support inference of benefit from active treatment for the efficacy endpoint being tested.

The estimand estimated by the primary linear contrast of the random-slopes linear mixed model is the difference in mean rate of progression of a given continuous efficacy endpoint in the active treatment group relative to the placebo group in the FAS population. The estimand is defined by the following attributes:

Treatment: pridopidine administered orally at a dosage of 45 mg BID vs. placebo.

Population: FAS population as defined in Section 6.1.

Variables: mean rate of change in endpoint from baseline to the Week 24 Visit.

Intercurrent event: treatment discontinuation: handled via treatment policy approach, all data will be used including data collected during the placebo-controlled period after treatment discontinuation. Missing data post-treatment will not be imputed, handled via missing at random assumption.

Population-level summary: difference in conditional mean slopes of active treatment relative to placebo.

Inference from this analysis is supportive of inference from the Bayesian shared-parameter, repeated-measures model for the primary endpoint and is primary for the secondary endpoint of rate of change in SVC. A separate supportive analysis will include centered baseline serum NfL level and the interaction of centered baseline serum NfL level and study month as additional covariates.

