- Efficacy Per-protocol (EPP) Set: The subset of participants in the FAS analysis set who initiated study treatment and who were not involved in protocol deviations related to eligibility, treatment, follow-up, or assessment, classified according to the treatment they actually received. Final specification of participants included vs. excluded from the EPP analysis set will be defined prior to data lock. Inclusion or exclusion from the EPP analysis set of any participant for whom treatment assignment was unblinded prior to data lock will be governed by the prespecified criteria above. If a participant's data is truncated for inclusion in the EPP analysis set due to a time-dependent event, e.g., initiation of a prohibited medication or non-adherence to protocol-specified dosing, clinical events observed up to 28 days after the censoring event will be included in the EPP analysis set. Data from placebo participants shared from other regimens will not be truncated due to non-adherence to protocol-specified dosing.

Applicable analysis sets (FAS, mITT, ECM, EPP, STF, and STN) will include shared placebo participants from regimens A, B, and C. As only concurrently enrolling regimens are contributing to efficacy analyses, the FAS and ECC analysis sets are synonymous in RGD and only the FAS analysis set will be referenced. As regimen A is administered by subcutaneous injection and regimens B and C are administered orally, only regimens B and C will contribute shared placebo participants to the ECM and STN analysis sets.

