6.5 Secondary Efficacy Analyses

6.5.1 Hierarchical Testing

Primary inference for secondary efficacy endpoints will be based on analysis of the FAS analysis set or subsets of the FAS analysis set as defined below. Primary estimates and inference for time-to-event endpoints will be by Kaplan-Meier product-limit estimates and log-rank test (see Section 6.5.6 below). Primary estimates and inference for responder endpoints will be by logistic regression as described in Section 6.5.5 with missing data handled as indicated in Section 3.6. Primary estimates and inference for rate of change of continuous endpoints will be by a random-slopes linear mixed model (see Section 6.5.3 below). The sequence for testing secondary efficacy endpoints is the following:

1. Time to first decline of 2 points or greater post-baseline in the ALSFRS-R total score among participants in FAS with bulbar dysfunction at baseline defined as an ALSFRS-R bulbar domain (Q1-Q3) score of less than 12,

2. Proportion of participants experiencing no worsening in the ALSFRS-R bulbar domain (Q1-Q3) score from baseline through Week 24 among all participants in FAS,
3. Rate of change in respiratory function as measured by slow vital capacity (SVC) maximum percent predicted from baseline through Week 24 among participants in FAS with bulbar dysfunction at baseline defined as an ALSFRS-R bulbar domain (Q1-Q3) score of less than 12,
4. Time to first decline post baseline of 1 point or greater in the ALSFRS-R bulbar domain (Q1-Q3) score among all participants in FAS, and
5. Time to death or death equivalent through Week 24 among all participants in FAS.

If the primary analysis indicates a significant slowing in disease progression from the Bayesian shared-parameter, repeated-measures model of ALSFRS-R and mortality, then each secondary efficacy endpoint in succession would be declared significant in the specified sequence using a comparison-wise criterion of two-tailed $p < 0.05$. After the first failure to declare significance, no endpoints lower in the hierarchy can be significant. This sequential closed-testing procedure controls the overall type 1 error rate at 5%. Nominal comparison-wise p-values for secondary efficacy endpoints will also be reported.

All secondary efficacy analyses specified here for hierarchical testing will also be analyzed in the mITT analysis set as sensitivity analyses.

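### The SVC slope test (key secondary 3) uses Wald inference with no small-sample method on a regimen variance estimated from four regimens, so its 5% level is not assured

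*SAP*

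**What the plan says.** SAP 6.5.1 lists as step 3 of the fixed sequence "Rate of change in respiratory function as measured by slow vital capacity (SVC) maximum percent predicted from baseline through Week 24", in FAS participants with bulbar dysfunction at baseline. Each step is tested at two-tailed 0.05, and the section states: "This sequential closed-testing procedure controls the overall type 1 error rate at 5" per cent.

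SAP 6.5.3 says that the random-slopes model "is primary for the secondary endpoint of rate of change in SVC". The model is fitted by REML with the regimen-level term "random intercept month / subject=regimen type=un". That is an unstructured 2×2 matrix with three parameters. The MODEL statement ends "NDX|month bulbar|month / solution cl", and the ESTIMATE statement carries only a request for confidence limits. Neither names a degrees-of-freedom method. Of the result, the text says: "The estimate and its 95% Wald confidence bounds will be obtained by a linear contrast of adjusted means".

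SAP 6.1 states that the analysis sets, including the FAS, "will include shared placebo participants from regimens A, B, and C". With regimen D that makes four regimens.

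**The concern.** All pridopidine participants are in D, while most placebo participants are likely to be in A to C. The slope contrast is therefore partly a comparison between regimens, and its standard error needs the regimen slope variance. Four units say little about a variance, and REML often returns exactly zero. A Wald test treats that estimate as known. When it is too small, the interval is too short and the p-value too low.

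Step 3 is a confirmatory claim and the gate to steps 4 and 5. A test that exceeds its level there weakens the stated control of the sequence.

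**Working it through.** **Inputs from the documents.** Two-sided 0.05 per step (SAP 6.5.1). Four regimens (SAP 6.1). 120 active and 40 placebo in D (protocol, RSA summary). SVC at baseline and Weeks 8, 16 and 24 (SAP 2.9).

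**Assumptions.** 40 placebo participants in each of A, B and C. Bulbar dysfunction in 100%, 50% or 30% of participants. Between-regimen slope SD equal to r times the participant-slope SD. No covariates and no dropout.

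**1. The plan's own figure.** A fixed sequence of tests, each of size 0.05 (critical value 1.960 for a z test), keeps the family-wise rate at 0.05. The claim is right if each test has that size.

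**2. Degrees of freedom.** No random effect in the code contains treatment × month. I assume the default method then uses residual df, that is observations minus the rank of the combined fixed and random design. With all participants this is 280 × 4 − 280 × 2 = 560. With half it is 280, and with 30% it is 168. The test is then close to a z test.

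**3. How regimen variance enters.** Take the participant-slope variance as 1. If the regimen variance is estimated at zero, placebos are pooled with equal weight, and the regimen part of the contrast is 0.75·a_D − 0.25·(a_A + a_B + a_C).
- Its variance is r²(0.5625 + 3 × 0.0625) = 0.75r².
- The sampling part is 1/120 + 1/160 = 0.01458, so the reported SE is about 0.121.
- At r = 0.2 the total variance is 0.01458 + 0.75 × 0.04 = 0.04458, an SD of 0.211.

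This overstates the average shortfall, because trials with a zero estimate are those in which regimens happened to look alike. Over all simulated trials at r = 0.2, the mean model SE was 0.149 against a true SD of 0.171.

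**4. Size of the printed test.** Null simulation on participant slopes, residual df, 40,000 trials per cell (Monte Carlo SE at most 0.15 points):

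| r | All participants | 50% | 30% |
|---|---|---|---|
| 0 | 5.1% | 5.2% | 5.5% |
| 0.05 | 6.1% | 6.1% | 5.5% |
| 0.1 | 7.8% | 7.1% | 6.6% |
| 0.2 | 9.6% | 8.8% | 8.3% |
| 0.3 | 8.8% | 9.6% | 9.7% |
| 0.5 | 7.2% | 8.2% | 9.1% |
| 1 | 5.7% | 6.4% | 6.9% |

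With all participants, the regimen variance was estimated at zero in 61% of trials at r = 0, 46% at r = 0.1 and 23% at r = 0.2.

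A check with the full structure of eqn. 2 (1,500 trials per cell, z test, SE 0.6 to 0.8 points) gave, for all participants and for half: 5.7% and 5.9% at r = 0; 8.8% and 7.4% at 0.1; 9.6% and 9.4% at 0.2; 9.4% and 9.5% at 0.3. A separate run of the slope model with 2,500 trials per setting was somewhat lower: 4.7 to 5.1% at r = 0, 4.9 to 6.6% at 0.05, and 7.4 to 8.7% at 0.1 to 0.3.

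**5. Alternatives.**
- Kenward-Roger, dropping a variance estimated at zero: 3.3 to 5.3%, 3.5 to 5.6% and 3.7 to 6.1% in three sets of runs. At r = 0 it is about 3.5%.
- Kenward-Roger, keeping that zero parameter in the information matrix: 0.2 to 2.6%.
- Satterthwaite df alone, r = 0.1 to 0.3: 6.3 to 7.8% (all participants) and 5.7 to 7.8% (half).
- Contrast within regimen D only: 4.9 to 5.3% at every r. Its SE is √(1/120 + 1/40) = 0.183, against about 0.13 with shared placebos and r = 0.

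**The case against.** **Regimens may hardly differ.** Participants are randomly assigned to regimens after common eligibility, stratified by riluzole and edaravone use (SAP 2.5). Only concurrently enrolling regimens contribute, and the model adjusts slopes for prognostic covariates that the simulations omit. RSA 9.3 expects no systematic differences between controls. This stands as an argument that r may be small, and at r = 0.05 the excess is about one point. It does not remove the point. RSA 9.3 speaks only of the primary endpoint, and the SAP itself allows for differences: it models regimen slopes, defines the ECM set because regimen A is subcutaneous, and compares controls across regimens in 6.5.13.

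**The master SAP may fill the gap.** It is not available here, and 6.5.11 sends some sensitivity analyses to it. But this SAP prints its own revised code and outranks the master SAP (section 1). Neither those analyses nor the imputation in 6.5.10 change the test that decides step 3.

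**The software default is assumed.** This is true. If the contrast received 2 or 3 df, size would be about 1% or less. The test would then be too strict, which is also a reason to state the method.

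**Step 3 may not be reached.** The excess matters only if the primary and steps 1 and 2 succeed on real effects while SVC is null. If they pass with probability p, independently of step 3, the family-wise rate is p × size. At 9.6% it exceeds 5% only when p is above 0.05/0.096 = 0.52. A claim of control must still cover that case.

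**The same fault in 6.5.2?** A reader might infer this, because 6.5.2 also uses Wald bounds and a regimen random effect. The documents do not support it. Eqn. 1 has only a regimen intercept, which cancels from a change-from-baseline contrast. With complete data and no covariates, the contrast SE was 1.7126 for regimen variances of 0, 1, 4, 25 and 100. No key secondary takes its primary inference from 6.5.2.

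**Conclusion.** The point holds for SAP 6.5.3 and key secondary 3. The printed test has a size of about 5% if regimens do not differ, and roughly 5 to 10% if the between-regimen slope SD is 0.05 to 0.3 of the participant-slope SD. This rests on that assumed SD, the assumed placebo counts in A to C, the assumed bulbar fraction, and residual df by default.

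A reader might go further and say that the type 1 error is doubled, or that 5% control has failed. The documents give no regimen SD, so neither follows. The inflation peaks near 10% in these settings and falls again at large r, to 5.7 to 6.9% at r = 1. What can be said is that the control stated in 6.5.1 is not assured at step 3. The Bayesian primary analysis is not affected.

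**What to change.** In SAP 6.5.3 only:
- Add ddfm=kr to the MODEL statement.
- Replace the Wald bounds with Kenward-Roger t-based bounds and p-values, and say that these decide step 3.
- State that a regimen variance estimated at zero is dropped from the degrees-of-freedom calculation. Without this rule, the result can range from near-nominal to very conservative.

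The change is one option and two sentences. The cost is slightly wider intervals and a mildly conservative test (about 3.5%) if regimens do not differ. The Kenward-Roger runs used a single regimen slope variance, not the printed 2×2 matrix, so a short simulation of the full model at the actual placebo counts would be a sensible check. A regimen-D-only SVC slope analysis (the ERO set) reported alongside would show whether the conclusion depends on shared placebos.

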6.5.4 Time to First Evidence of Bulbar Dysfunction

The time to first evidence of bulbar dysfunction will be compared between treatments by Kaplan-Meier product-limit estimates and log-rank test in the subset of participants with an ALSFRS-R bulbar domain (Q1-Q3) score of 12 at the Baseline Visit in the FAS, mITT, ERO, and EPP samples. If greater than 10% of participants develop bulbar dysfunction after baseline, treatments will be compared by Cox proportional hazards regression adjusting for time since ALS symptom onset, delta-FRS, use of riluzole at baseline, use of edaravone at baseline, and use of Nuedexta at baseline with a random gamma-distributed regimen-specific frailty term. If convergence is not obtained, then the frailty term will be dropped. A separate supportive analysis will include centered baseline serum NfL level as an additional covariate.

6.5.5 Responder Analysis

Analysis of responder endpoints will use logistic regression. The dependent variable will be whether the participant is a responder or not, while the independent variables will be treatment group, baseline ALSFRS-R score, site of onset (any bulbar vs. non-bulbar), riluzole use at baseline, edaravone use at baseline, and delta-FRS. A separate supportive analysis will include centered baseline serum NfL level as an additional covariate.

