9.4 Secondary Efficacy Endpoints

If the primary analysis demonstrates significant slowing of decline in ALSFRS-R among participants randomized to pridopidine, then the following secondary hypotheses will be tested in the specified sequence with overall type I error rate controlled using a sequential closed-testing procedure:

1. Rate of change in ALSFRS-R bulbar subdomain (Q1-Q3) score among participants with bulbar dysfunction at baseline,
2. Rate of change in ALSFRS-R bulbar subdomain (Q1-Q3) score among all randomized participants,
3. Rate of change in the speech sub-score of the ALSFRS-R (Q1) among all randomized participants
4. Rate of change in SVC maximum percent of predicted among all randomized participants,
5. Rate of change in ALSFRS-R bulbar subdomain (Q1-Q3) score among participants with pre-baseline slope ≥ 0.75 points/month,
6. Time to onset of bulbar symptoms among participants free of bulbar dysfunction at baseline,
7. Rate of change in HHD percent change from baseline among all randomized participants,
8. Time to death or death equivalent

Analyses for each secondary hypothesis will use an ITT analysis sample that includes placebo participants from concurrently enrolling regimens. Analyses of ALSFRS-R bulbar subdomain,

CNS-BFS, HHD, and SVC will use shared-baseline linear mixed models that adjust for time since onset of weakness, pre-baseline slope, baseline riluzole use, baseline edaravone use, baseline Nuedexta use, and site of onset and their interactions with time since baseline, and include random intercepts and slopes by regimen and by participant with unstructured covariance at each level. Given low expected event rates, time to bulbar onset and time to death or death equivalent will use log-rank tests. Per protocol analyses will also be performed to evaluate the effects of pridopidine on participants complying with study regimen. Details of endpoint measures, analysis samples, statistical models, and the closed-testing procedure will be described in the regimen-specific statistical analysis plan.

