2.6 Treatment Allocation

Participants in RGD are randomly allocated in a 3:1 ratio to pridopidine 45 mg BID or placebo treatment based on a pre-specified permuted-block randomization schedule, stratified by use of riluzole, edaravone, both, or neither at the time of screening for the Master Protocol.

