- Time to first decline of 1 or more points post baseline in the ALSFRS-R bulbar domain (Q1-Q3) score among participants in FAS with bulbar dysfunction at baseline defined as an ALSFRS-R bulbar domain (Q1-Q3) score of less than 12,
- Proportion of participants experiencing no worsening in the ALSFRS-R bulbar domain (Q1-Q3) score from baseline through Week 24 among all participants in FAS with delta-FRS slower than -0.75 points/month (slow progressors),
- Proportion of participants with ALSFRS-R bulbar domain (Q1-Q3) score greater than or equal to 9 (out of 12) at Week 24 among all participants in FAS with bulbar dysfunction at baseline defined as an ALSFRS-R bulbar domain (Q1-Q3) score of less than 12,

- Proportion of participants experiencing no worsening in the ALSFRS-R bulbar domain (Q1-Q3) score from baseline through Week 24 among all participants in FAS with baseline ALSFRS-R greater than or equal to 36 (Early in disease),
- Rate of change in CNS-BFS total score from baseline through Week 24 among all participants in FAS,
- Rate of change in CNS-BFS total score from baseline through Week 24 among participants in FAS with bulbar dysfunction at baseline defined as an ALSFRS-R bulbar domain (Q1-Q3) score of less than 12,
- Change in HHD upper extremity percentage from baseline through Week 24,
- Change in HHD lower extremity percentage from baseline through Week 24,
- Change in log transformed serum NfL from baseline through Week 24 among all participants in FAS,
- Change in log transformed serum NfL from baseline through Week 24 among participants in FAS with bulbar dysfunction at baseline defined as an ALSFRS-R bulbar domain (Q1-Q3) score of less than 12,
- Change in log transformed serum NfL from baseline through Week 24 among participants in FAS by NfL median baseline split (slow vs fast progressors),
- Rate of change in ALSFRS-R total score from baseline through Week 24 among participants in FAS who were not on Nuedexta at baseline,
- Rate of change in ALSFRS-R total score from baseline through Week 24 among participants in FAS who were not on Nuedexta at baseline and with bulbar dysfunction at baseline defined as an ALSFRS-R bulbar domain (Q1-Q3) score of less than 12,
- Rate of change in CNS-BFS total score from baseline through Week 24 among participants in FAS who were not on Nuedexta at baseline,

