6.5.10 Placebo Multiple Imputation

Placebo multiple imputation analyses are the same as specified in the M-SAP with the addition of baseline serum NfL level as a covariate and will be applied to the mixed model repeated-measures analysis of ALSFRS-R total score and the random-slopes analysis of SVC in the FAS analysis set.

The following SAS code specifies the imputation for an endpoint measured every 8 weeks:

```
proc mi data=work.outcomes seed=xxx nimpute=50 out=work.out_mi01
    minimum=. . . . . x x x x maximum=. . . . . y y y y minmaxiter=1000;
    class rlz edv trtrnd;
    fcs reg(Wk08 = sx2b1 dFRS rlz edv Wk00);
    fcs reg(Wk16 = sx2b1 dFRS rlz edv Wk00 Wk08);
    fcs reg(Wk24 = sx2b1 dFRS rlz edv Wk00 Wk08 Wk16);
    mnar model( Wk08 Wk16 Wk24 / modelobs=(trtrnd="0"));
    var sx2b1 dFRS rlz edv Wk00 Wk08 Wk16 Wk24;
run;
```

where Wk00, Wk08, Wk16, and Wk24 are the values of a given efficacy endpoint at the Baseline, Week 8, Week 16, and Week 24 Visits, respectively, trtrnd has a value of zero (0) for participants randomized to placebo, and x and y take appropriate values to specify the range of a given outcome measure (i.e., 0 and 48 for ALSFRS-R total score; 0 and . for HHD upper and lower extremity percentages and SVC).

Inference from these analyses is supportive of inference from the Bayesian shared-parameter, repeated-measures model for the primary endpoint and assess sensitivity to the missing data assumption of the random-slopes linear mixed model for SVC in the FAS analysis set. A separate analysis will include centered baseline serum NfL level as an additional covariate in both imputation stages.

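### SAP 6.5.5 does not name the endpoint's own baseline score for seven of the ten responder endpoints, key secondary 2 among them (free improvement, minor)

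*SAP*

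**What the plan says.** SAP 6.5.1 makes the model primary: "Primary estimates and inference for responder endpoints will be by logistic regression as described in Section 6.5.5". SAP 6.5.5 gives its covariates as "treatment group, baseline ALSFRS-R score, site of onset (any bulbar vs. non-bulbar), riluzole use at baseline, edaravone use at baseline, and delta-FRS". The only variant is a supportive analysis that adds baseline serum NfL.

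The second test in the fixed sequence of SAP 6.5.1 is a responder endpoint: "Proportion of participants experiencing no worsening in the ALSFRS-R bulbar domain (Q1-Q3) score from baseline through Week 24 among all participants in FAS". The sequence is strict: "After the first failure to declare significance, no endpoints lower in the hierarchy can be significant". Below key secondary 2 stand the rate of change in SVC, time to bulbar decline, and survival.

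SAP 4.1 also lists, outside the multiplicity-adjusted set, "Proportion of participants with ALSFRS-R bulbar domain (Q1-Q3) score greater than or equal to 9 (out of 12) at Week 24" among participants with bulbar dysfunction at baseline.

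Treatment allocation (SAP 2.6) is "stratified by use of riluzole, edaravone, both, or neither at the time of screening for the Master Protocol", so bulbar score is not balanced by design.

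**The concern.** A responder endpoint defined by change on a scale, or by reaching a level on it, usually depends on where the participant started on that scale. If the model adjusts for a different baseline score, some explainable variation stays unexplained, and a chance difference between arms in the right score is only partly corrected.

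For key secondary 2 the stake is a little power at a point where a miss closes three further tests. For the endpoint of 9 or more at Week 24 the dependence is direct: a participant who starts at 11 can lose 2 points and still respond, while one who starts at 6 must gain 3.

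**Working it through.** **1. Count of responder endpoints (SAP 4.1 and 4.2).**

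| Scale | Endpoints | Number |
|---|---|---|
| Bulbar domain | key secondary 2; at most a 1-point decline (bulbar dysfunction); no worsening in slow progressors; 9 or more at Week 24; no worsening with baseline total of 36 or more; no worsening in fast progressors (exploratory) | 6 |
| ALSFRS-R total | decline of 5 points or less: all FAS, baseline 36 or more, bulbar dysfunction | 3 |
| CNS-BFS total | no worsening among participants not on Nuedexta | 1 |

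The total is 10: one key secondary, eight other secondary and one exploratory. Endpoints not on the total score: 6 + 1 = 7.

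**2. Which score 6.5.5 means.** The score is unqualified. SAP 4.1 uses an unqualified baseline ALSFRS-R with a threshold of 36, which only the total can reach because the bulbar domain stops at 12. The SAP labels bulbar scores as bulbar domain (Q1-Q3). The total is therefore the natural reading, though not a certain one. No reading covers the CNS-BFS baseline.

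**3. Own baseline elsewhere in the SAP.** In the imputation code of SAP 6.5.10, "Wk00, Wk08, Wk16, and Wk24 are the values of a given efficacy endpoint at the Baseline" and later visits, and Wk00 predicts each of them. The contrast in SAP 6.5.2 treats the baseline visit as one of the repeated outcomes, so that model uses the endpoint's baseline without a covariate. A logistic model of one binary result per participant uses it only if it is listed.

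**4. Size for key secondary 2.** The documents state no power or response rate for any responder endpoint, so there is no figure to reproduce.

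- From the documents: 120 active and 40 placebo within the regimen; two-sided 5%.
- Assumed: 160 placebo in all (40 from each of four regimens); treatment odds ratio 2; 25% bulbar onset; 40% at bulbar score 12; 15% on Nuedexta with odds ratio 0.67; 5% set to non-responder for death or progression.
- Model: log-odds of response = constant + log(2) × treatment + g × bulbar score + other covariates. Both analyses were fitted to the same 6,000 data sets per setting; the simulation error of each difference is 0.4 points or less.

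| g per bulbar point | Power, SAP list | Power, plus bulbar score | Gain (points) |
|---|---|---|---|
| -0.15 | 0.757 | 0.757 | 0.0 |
| 0 | 0.751 | 0.753 | +0.2 |
| +0.15 | 0.734 | 0.741 | +0.7 |
| +0.30 | 0.701 | 0.716 | +1.5 |
| +0.45 | 0.644 | 0.672 | +2.8 |

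With no treatment effect, rejection was 4.6-5.5% on the SAP list and 4.7-5.6% with the score added. With 100 placebo (3,000 runs) the gain was +0.4 at g = 0.15 (0.626 to 0.630) and +2.1 at g = 0.45 (0.569 to 0.590).

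**5. Chance imbalance.** A one-SD chance difference in mean bulbar score was about 0.22 points. Since √(1/120 + 1/160) = 0.121, this implies an SD of about 0.22/0.121 = 1.8 points. Such a difference multiplied the estimated odds ratio by 0.982-1.049 under the SAP list and by 0.995-1.003 with the score added.

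**6. A cruder second simulation.** It assumed response of 45% v 60%, 160 placebo, and no site of onset or delta-FRS in the model. At a log odds ratio of 0.4 per SD of own baseline, power rose from 0.714-0.718 to 0.728-0.733. At 0.8 it rose from 0.711-0.729 to 0.760-0.762. At 1.5 it rose from 0.719-0.734 to 0.834-0.842. With an SD of 1.8, g = 0.45 is about 0.8 per SD, so the middle case corresponds to the last row above. The case of 1.5 is about 0.83 per point, more than 100-fold in odds across six points, and is not used.

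**7. Unconditional value.** Key secondary 2 is tested only if the primary analysis and key secondary 1 both succeed. If that has probability 0.2, 0.5 or 0.8 (assumed), a 3-point gain is worth 0.6, 1.5 or 2.4 points.

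**8. Bulbar score of 9 or more at Week 24.** Assumed: 60% below 12 at baseline, so 72 v 96, with 10%, 20% or 30% starting below 9 (2,000 runs).

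| Assumed slowing | 10% below 9 | 20% | 30% |
|---|---|---|---|
| 50% | 0.486 to 0.577 | 0.415 to 0.522 | 0.349 to 0.477 |
| 35% | 0.229 to 0.290 | 0.224 to 0.288 | 0.182 to 0.234 |

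The gain is about 5 to 13 points, with rejection under no effect of 5.0-5.9% in both models. A separate run under other assumed inputs gave about 12 to 20 points, with no failed fits in 2,000 runs per setting.

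**The case against.** The strongest reply is that nothing is wrong here. The model is pre-specified, valid, and already adjusts for an ALSFRS-R score, site of onset, delta-FRS and both stratification factors. Key secondaries 1, 4 and 5 are tested by log-rank, so the responder model is already more adjusted than most of the hierarchy. The unqualified score could mean the domain score for the bulbar endpoints, and the Master SAP, which holds the score definitions, was not available to check. The imputation code serves the ALSFRS-R total and SVC and sets no rule for analysis covariates. The top of the range needs g = 0.45, about 15-fold odds between bulbar scores of 6 and 12 (exp(6 × 0.45) = exp(2.7) = 14.9).

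Most of this stands, and it is why the point is minor. It does not remove the CNS-BFS gap, and doubt about which score is meant is itself a reason to name it. Extra terms could strain the small subsets, and SAP 7.2 omits analyses that fail to converge. No fit failed in simulation, but a stated fallback is sensible.

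A reader might also infer that leaving out baseline Nuedexta use costs power or breaks the SAP's own rule. The documents do not support that. Protocol 9.4 plans to adjust for "baseline edaravone use, baseline Nuedexta use, and site of onset and their interactions with time since baseline", but in linear mixed models, and SAP section 1 ranks the SAP above the protocol appendix on secondary analyses. The Cox model in SAP 6.5.4 is fitted only if more than 10% develop bulbar dysfunction, and it serves an exploratory endpoint. The adjusted CAFS and the imputation code also leave Nuedexta out. In simulation, Nuedexta alone added 0.3 to 0.5 points, close to simulation error; a separate check gave -0.3 to +0.7. A gain of 1.9 appeared only with both 30% use and an odds ratio of 0.45 assumed.

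**Conclusion.** The point holds as a free, minor improvement. The gap in the covariate list is read directly from the text: certain for the CNS-BFS endpoint, and the natural reading for the six bulbar endpoints.

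For key secondary 2 the benefit is 0 to about 3 power points if reached, and less unconditionally. This rests on assumed response rates, bulbar distribution, gradient and shared-placebo count. For the endpoint of 9 or more at Week 24 the gain is larger (about 5 to 20 points across the assumed settings), but that endpoint is not multiplicity-adjusted and does not set the severity.

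A reader might take the omission to bias the test or inflate type I error. It does neither: rejection under no effect stayed near 5% with and without the added score.

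**What to change.** In SAP 6.5.5, before unblinding:

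- Name the listed score as the ALSFRS-R total.
- Add the baseline value of the scale that defines each endpoint: the bulbar domain (Q1-Q3) score for the six bulbar endpoints and the CNS-BFS total for the CNS-BFS endpoint. The three total-score endpoints need no addition.
- State that a model that does not converge falls back to the current list, so that SAP 7.2 does not drop the analysis.
- Optionally add baseline Nuedexta use, for consistency with the mixed models, except where the endpoint is already restricted by it.

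The cost is a few lines of text and one more parameter per affected model. No new data are needed: both scales are scheduled at the Baseline Visit, and an endpoint of no worsening in CNS-BFS already needs its baseline, including for any shared placebo participant who contributes. An added covariate changes the conditional odds ratio being estimated, which is why the change must be settled before unblinding. Where the bulbar score had no effect, adding it cost no power in simulation (+0.2 points).
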